4.2.2. Data on Scrambler therapy

In 2018, the Johns Hopkins Neuromyelitis Optica Clinic conducted a sham-controlled randomized trial of Scrambler treatment over 10 consecutive days in 22 NMOSD patients to determine efficacy, acceptability, feasibility and duration of in-clinic therapy. We measured changes in pain with the numerical rating scale and analyzed change in pain levels and related symptoms at time of treatment and again at 30 and 60 days. The findings showed significant pain reduction and quality of life improvements, including reduction of anxiety and depression, up to 30 days. Scrambler has been used in other patients with central neuropathic pain including a brainstem lesion and transverse myelitis.

Because of the positive effects of Scrambler therapy on NMOSD patients, and because of the complications inherent in accessing said therapy, we became interested in following that study with one assessing portable devices using similar methodology.

TENS for Neuropathic Pain in NMOSD

Principal Investigator: [name], PhD

4.2.3. Data on Quell Relief

In a study for Quell TENS on back pain, the following results were reported:

“After six weeks, those in the Experimental group reported lower “worst” pain scores and less overall interference than those in the Control group ($p<0.025$). After three months those assigned to the Experimental group (hfTENS device) reported significantly less pain (worst, least, average, now) than those in the Control condition ($p<0.01$; Table 3). Pre-post comparisons on average pain intensity on the BPI showed significant groups differences (Experimental=1.24; Control=-0.03; $t=2.74$; $p<0.01$) with 31.0% of the Experimental group showing ≥ 2.0 differences vs. 12.9% among the Control group. Those in the Experimental group also reported less overall pain-related interference (general activity, mood, walking ability, work, relation with others, sleep, and enjoyment of life) compared with the Control group ($p<0.025$). Also, subjects assigned to use the hfTENS reported reduced pain catastrophizing scores compared with the Controls ($p<0.025$). No differences were noted between groups on the self-report questionnaires assessing disability (PDI) and anxiety and depression (HADS). Both groups demonstrated a reduction in the use of prescription pain medication, but no differences were found between groups.”

TENS for Neuropathic Pain in NMOSD

Principal Investigator: [name], PhD

5. Patient Population

5.1. Inclusion Criteria

- 5.1.1. Men and women 18 years of age or older diagnosed with NMOSD per the 2015 NMOSD criteria
- 5.1.2. Patients must be positive for the aquaporin-4 antibody in serum
- 5.1.3. Presence of persistent neuropathic pain (≥ 3 months) rated at a level of 4 or higher on the Numerical Pain Scale
- 5.1.4. Patients must be stable in their disease, such that they have had no spinal cord relapses within 6 months prior to enrollment
- 5.1.5. Patients must be on a stable medication regimen that may include anti-epileptic, antidepressant, or non-steroidal anti-inflammatory medications, with no adjustments to the regimen within 30 days of enrollment
- 5.1.6. Pain must be localized to a spinal cord lesion
- 5.1.7. Patient understands the study regimen, its requirements, risks, and discomforts, and is able and willing to sign an informed consent form
- 5.1.8. Patients must own and be able to operate an iOS or Android smartphone with internet connection

5.2. Exclusion Criteria

- 5.2.1. Patients who are cognitively or mentally incompetent
- 5.2.2. Patients whose primary complaint is numbness/tingling
- 5.2.3. Any of the following: pregnant women, nursing women, women of childbearing potential or their sexual partners who are unwilling to employ adequate contraception

TENS for Neuropathic Pain in NMOSD

Principal Investigator: [name], PhD

(condoms, diaphragm, birth control pills, injections, intrauterine device [IUD], surgical sterilization, subcutaneous implants, abstinence, etc.).

- 5.2.4. Use of an investigational agent for pain control concurrently or within the past 30 days
- 5.2.5. History of an allergic reaction or previous intolerance to transcutaneous electronic nerve stimulation or to latex
- 5.2.6. Patients with implantable drug delivery systems, e.g. Medtronic Synchromed.
- 5.2.7. Patients with heart stents or metal implants such as pacemakers, automatic defibrillators, cochlear implants, aneurysm clips, vena cava clips and skull plates (Metal implants for orthopedic repair, e.g. pins, clips, plates, cages, joint replacements are allowed)
- 5.2.8. Patients with a known history of myocardial infarction or ischemic heart disease within the past six months
- 5.2.9. Patient who have had surgery to treat a pain-related condition in the last 6 months
- 5.2.10. Prior celiac plexus block, or other neurolytic pain control treatment, within 1 month
- 5.2.11. Other identified causes of painful parasthesias existing prior to chemotherapy (e.g., carpal tunnel syndrome, B12 deficiency, AIDS, monoclonal gammopathy, diabetes, heavy metal poisoning amyloidosis, syphilis, hyperthyroidism or hypothyroidism, inherited neuropathy, etc.) that might be responsible for the patient's current neuropathic symptoms
- 5.2.12. Skin conditions such as open sores that would prevent proper application of the electrodes
- 5.2.13. Patients with an ongoing concomitant central neurologic disorder or history of epilepsy, brain damage, or symptomatic brain metastases
- 5.2.14. Other medical or other condition(s) that in the opinion of the investigators might compromise the objectives of the study
- 5.2.15. Pain is primarily due to prior spinal fusion procedure or pain is in an area where there was previously a spinal fusion procedure

TENS for Neuropathic Pain in NMOSD

Principal Investigator: [name], PhD

5.2.16. History of an allergic reaction or previous intolerance to hydrogel adhesive used in TENS devices

5.2.17. Patients with implantable spinal cord stimulators

5.3. Inclusion of Women and Minorities

This interventional clinical trial will involve the recruitment of 46 participants with central neuropathic pain resulting from neuromyelitis optica spectrum disorder (NMOSD). There are no restrictions related to sex, race or ethnicity for trial inclusion. NMOSD disproportionately affects women and minorities. Given that the ratio by sex of those diagnosed with NMOSD is 6.5-9 females for every 1 male, the expectation is that at least 80% of participants will be women.

5.4. Inclusion of Children

This study includes women and men with central neuropathic pain caused by neuromyelitis optica spectrum disorder (NMOSD) who are of age 18 years or older. Because previous trials have involved those aged 18 and older, children under the age of 18 will not be included. Most patients are diagnosed with NMOSD in their 30's and 40's, and it is the expectation that this will impact recruitment very little.

TENS for Neuropathic Pain in NMOSD

Principal Investigator: [name], PhD

6. Study Design and Treatment Plan

6.1. Summary

Building on the recent successful phase II study using Scrambler TENS among NMOSD patients, we propose bringing a non-invasive neuromodulation technology to a larger NMOSD population with the important distinction that we will study self-administered take-home QUELL FLEX units on this cohort of patients for the reasons outlined above.

6.2. Recruitment

We plan to recruit 46 consecutive patients with NMOSD (23 per arm) with a diagnosis of NMOSD based on the 2015 international consensus diagnostic criteria and the presence of neuropathic pain. Trial information will be made available through clinicaltrials.gov.

6.3. Determination of Eligibility

Eligibility for participation will be reviewed and confirmed by a member of the study staff. Upon successful eligibility, the patient will be eligible for registration into the study, at which time a study-specific subject ID/number will be assigned.

For patients who reach the study team from outside of the Mass General NMO Clinic, a member of the patient's care team will be consulted to confirm that s/he believes that the participant is appropriate for protocol participation.

Study intervention cannot begin until the patient is successfully registered and consented.

6.4 Randomization and Blinding

Randomization would be done in blocks of 4 (e.g. 2 placebo and 2 treatment assignments) assigned at random at the beginning of the study for each 4 patients enrolled in the study consecutively. This ensures that it is not possible to predict the arm assignment of patients as we unblind them in groups of 4 at the conclusion of each patient's participation in the study.

Blinding keys, including the arm assignment of the patient, will be sealed in envelopes and not opened until unblinding occurs for the 4-patient-block.

6.5. Methods and Intervention

6.5.1. QUELL FLEX Transcutaneous Electrical Nerve Stimulation Therapy

The locations of symptoms will be assessed remotely by telemedicine and remote MRI review. If patient has pain areas referable to more than one lesion, treatment will be done on the area that is most bothersome to the patient.

6.5.1.1. Treatment Days

1. Prior to initiation of Quell therapy, patients will be asked to rate their pain on the Numerical Pain Scale and will complete a Short Form-36 Health Inventory (SF-36).
2. All training on the use of the device will be conducted remotely through Zoom.

TENS for Neuropathic Pain in NMOSD

Principal Investigator: [name], PhD

3. Patients will be shipped a QUELL FLEX device. It will either be a functional QUELL FLEX device for the treatment arm or a non-functional QUELL FLEX device in the sham arm. All of the lights, charging equipment, and app connectivity will be the same. The only difference is that the non-functional sham devices will administer an electrical current for only 2 minutes each at the top of a treatment hour, at 30 minutes and at 58 minutes, as opposed to for the full hour when the device is engaged.
4. Patients will be informed that we are conducting a number of different treatment paradigms – some of them have high frequency waves that are not perceptible, and some have lower frequency waves that may be transiently perceptible. In addition, we will re-inform them there is a sham arm.
5. The electrodes will be placed on patients on the back in the dermatome of the most painful area. The intensity of the stimulus is increased until the patient can first feel some sensation associated with the electrodes. Script: “Tell me when you feel something.”
6. Stimulation intensity will be increased until a maximum threshold is tolerated without being painful.
7. Once the intensity is at its maximum setting, the study coordinator will evaluate the level of pain. If the patient feels a constant burn, single sting or feeling of discomfort, the electrodes will be repositioned. The exact electrode positioning will depend on the delimitation of the surface pain area, and analgesic response of the patient.
8. Once satisfactory electrode placement and stimulus intensity is determined, therapy is maintained for at least an hour per day for 4 weeks (both treatment and sham groups).
9. Patients will report pain scores weekly throughout experimental period while on a zoom call with the trial researcher. Patients will again complete all measurement tools and pain ranking at end of treatment.
10. At the conclusion of the 4-week experimental arm, all patients will be shipped a new QUELL FLEX device for use in the 4-week open label phase. This one will be functional. The experimental QUELL FLEX devices will be returned in the same shipping box to the study team. Study staff will administer the SF-36 Quality of Life questionnaire.
11. In the 4-week open label phase, patients will continue to use the device with the electrodes in the same position. Weekly pain scores will be documented as before as well as the SF-36 Quality of Life questionnaire at the conclusion of the 4-week open label period.
12. At the conclusion of the 4-week open label period for the 4-patient block, blinding will be unsealed and reported to the patients. They will then have the opportunity to keep the functional QUELL FLEX if they wish.
13. Four and eight weeks after the completion of the open label phase, patients will be called for a wellness check and asked to rate their pain again.
14. Adverse Events will be monitored and documented weekly.

6.5.1.2. Treatment follow-up:

Patients will be contacted by Zoom weekly during the experimental and open-label phases to check in on them, and will be asked weekly to report their pain score. At the conclusion of the experimental phase and at the end of the study, patients will be asked again to complete the Short Form-36 Health Inventory (SF-36).

[figure not shown]
TENS for Neuropathic Pain in NMOSD

Principal Investigator: [name], PhD

Patient-Reported Outcomes

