Recently we completed a sham-controlled trial using a TENS unit called Scrambler in NMOSD patients showing a meaningful reduction in neuropathic pain compared to controls. The Scrambler device must be operated in an office by a professional technician, thereby limiting its usefulness to the wider NMOSD population. The Quell transcutaneous electrical nerve stimulation device delivers varying electric pulses non-invasively to reduce pain. It is a small, wearable device that utilizes regularly-changing electric pulses to stimulate nerves such that the experience of pain is blocked. Because the Quell Flex is programmable remotely, a sham-controlled trial can be conducted while keeping the patient blinded to the trial arm.

For patients with NMOSD and other conditions that cause pain originating in the central nervous system, non-obtrusive, non-pharmacological devices might prove a viable alternative to pain medications. Pharmaceutical treatments for pain such as opioids have led to addiction and life-style changes with unacceptable side effects. Cost and side effects are concerns with other pharmacologic therapies for pain. In addition, in efforts to control pain, many patients are prescribed multiple medications, and then have to cope with the complexities and hazards of polypharmacy. Most importantly, none of the pharmaceutical treatments for pain in NMOSD have been proven effective in a trial.

TENS for Neuropathic Pain in NMOSD

Principal Investigator: [name], PhD

If we could show among a significant patient cohort that a safe and effective at-home nonpharmacological pain therapy is available for patients with NMOSD, it would be life altering for a great many – not only those with NMOSD, but also with related neuroimmune disorders and other conditions with central neuropathic pain.

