6.6.1. General

The numerical pain scale will be administered verbally during each study visit.

Study staff will ask both average and worst pain experienced in the week prior to each study visit, using the same Numerical Rating Scale. Additionally, she will ask if and for how long relief lasted after QUELL FLEX use on average over the week.

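### Sham delivers current for 6 of 60 minutes against the full hour on active, but the plan never checks whether blinding held and does not say that the staff who take the verbal pain score are blinded or separate from set-up

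*Combined protocol and SAP*

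**What the plan says.** Stimulation (section 6.5.1.1):

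- Step 3: "the non-functional sham devices will administer an electrical current for only 2 minutes each at the top of a treatment hour". Further 2-minute bursts follow half-way through and 58 minutes in. On active, current runs throughout the hour.
- Steps 5 and 6: intensity goes past first sensation, and then "Stimulation intensity will be increased until a maximum threshold is tolerated without being painful". No distinction between arms is made.
- Step 7: the study coordinator evaluates pain at the maximum setting, and electrodes may be moved.

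Masking:

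- Step 3: lights, charging equipment and app connection are the same in both arms.
- Step 4: patients hear that some paradigms cannot be felt and that "some have lower frequency waves that may be transiently perceptible". They are also reminded that there is a sham arm.
- Section 6.4: assignments are in sealed envelopes until a block of four is finished.
- The introductory text before section 2 says that "a sham-controlled trial can be conducted while keeping the patient blinded to the trial arm". It says nothing about blinding of staff.

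Scoring:

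- Section 2.2: the primary outcome is the change in the 0–10 pain score from the screening call to week 4.
- Section 6.6.1: "The numerical pain scale will be administered verbally during each study visit". In the same section, staff also ask whether relief followed device use and how long it lasted.
- The person taking the score is the trial researcher in step 9 and study staff in section 6.6.1. Section 9.2 gives the weekly check-in to the study coordinator.

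Sections 11.1 to 11.4 contain no analysis of blinding, and Appendix A holds only the SF-36.

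**The concern.** A patient titrated to the strongest comfortable level, and aware that a sham exists, may draw a conclusion when current stops after 2 minutes. Set-up is the most exposed moment: titration, pain evaluation and possible repositioning may take longer than the first burst, with patient and staff on the same call. Sealed envelopes give no protection against that.

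The primary outcome is a spoken self-rating, so it is open both to the patient's expectation and to the way the question is put. If the blind failed, part of the difference between arms would be reporting bias. The trial would hold no data with which to assess that objection, and such data cannot be collected once the open-label device has been sent and the arms have been disclosed.

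**Working it through.** **Stimulation time.** Three bursts of 2 minutes (step 3): 3 × 2 = 6 minutes, and 6/60 = 10%. Over 28 days at one hour a day (step 8 sets at least an hour daily for 4 weeks), sham gives 28 × 6/60 = 2.8 hours of current and active gives 28.

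**Who sets up and who scores.** Step 7 places the coordinator at set-up. Section 6.5.1.2 has the pain score asked at the weekly contact, and section 9.2 has the coordinator hold that contact. Together these suggest that one person does both, but no sentence says so.

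**Inputs for the illustration.** Section 11.2 gives 19 evaluable patients per arm, a two-sample t-test, a 2.0-point effect and power 0.90. Alpha and sidedness are not stated; I assume two-sided 5%. The SD is given as about 20% without a base. I use 1.5 (the top of the range quoted for the original pain value), 2.0 (20% read as 2 points on the scale) and 1.85.

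**The plan's own figure.** At two-sided 5% and 19 per arm, power for 2.0 points is 0.85 with SD 2.0, 0.90 with SD 1.85 and 0.98 with SD 1.5. The stated 0.90 is therefore recovered at SD 1.85. The present point does not depend on it.

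**Net bias under assumed guessing.** No document figure exists for any of these inputs. Suppose a patient who infers an arm shifts the rating by 0.5 points, downwards if the guess is active and upwards if sham.

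- 60% guess right, 40% guess wrong: 2 × (0.60 − 0.40) × 0.5 = 0.2 points.
- 60% guess right, the rest do not shift: 2 × 0.60 × 0.5 = 0.6 points.
- All guess right: 2 × 1.00 × 0.5 = 1.0 point.

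**False-positive rate with no true effect.** Two-sided t-test, 36 degrees of freedom, noncentrality = (bias/SD) × √(19/2). For example, 0.6/1.5 × 3.082 = 1.233, which gives 22%.

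| Net bias | SD 1.5 | SD 1.85 | SD 2.0 |
|---|---|---|---|
| 0.2 | 7% | 6% | 6% |
| 0.6 | 22% | 16% | 15% |
| 1.0 | 52% | 37% | 32% |

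**Precision of a guess question.** The 95% half-width for a proportion of 50% is 1.96 × √(0.25/n): 22 percentage points with n = 19 and 20 with n = 23.

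**The case against.** The protocol does take masking seriously. The devices look and connect alike, the keys are sealed, and the cover explanation gives a patient who feels only brief stimulation a reason other than sham. These measures may be enough. They stand as a defence of the design, but they do not show that the blind held.

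A reader might infer more than the text supports in four ways:

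- *That active patients feel stimulation all hour and sham patients for a tenth of it.* The text gives minutes of current, not of sensation. Titration makes sensation at set-up likely; nothing says that it lasts.
- *That the coordinator who sets up the device takes the primary score.* This is plausible from sections 6.5.1.2 and 9.2, but the scorer is never named as the coordinator, and steps 5 and 6 do not say who raises the intensity. Attending set-up is also not the same as knowing the arm.
- *That set-up reveals a sham.* The bursts are defined within a treatment hour, while titration comes before therapy is maintained in step 8. Whether the burst schedule runs during titration is not stated, so this is a gap in the text and not a demonstrated leak.
- *That the false-positive rate is inflated by a known amount.* The bias sizes are assumptions, and with offsetting wrong guesses the rate stays close to 5%.

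It is also tempting to adjust the primary analysis for the guess. That would condition on a variable measured after randomisation that may itself reflect benefit. If most patients guessed correctly, guess and arm would be nearly collinear.

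**Conclusion.** The point holds in a limited form. Three things are established from the text: current runs for 10% of the hour on sham against all of it on active; no part of the readable plan assesses blinding; and a subjective primary score is taken by voice by staff whose blinding and separation from set-up are not stated. That blinding fails is not established, nor is the size of any bias. The false-positive range, from 6% at a net bias of 0.2 points to 52% at 1.0, shows only how sensitive a trial of this size would be. It rests on assumed biases, SD 1.5 to 2.0, 19 per arm and a two-sided 5% test. This is an inexpensive improvement to the credibility of the primary result and does not invalidate the design.

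**What to change.** 1. In sections 6.5.1.1 and 6.6.1, replace verbal administration of the pain score with patient self-entry by survey link before each call, at baseline and weekly. REDCap, or the other approved platform that section 10.2 allows for consent, could carry it. Allow a verbal score for patients who cannot enter it, and record it as such.
2. At the week-4 contact, after the pain score is recorded and before the open-label device is shipped, ask the patient and the staff member separately to guess the arm (active, sham, don't know) and to give the reason. In section 11, state that the answers will be tabulated by arm descriptively, and that the primary analysis will not be adjusted for them.

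The text should also state whether the staff who collect scores are blinded and separate from set-up, and whether sham current continues during titration. No change to the sham schedule is proposed.

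The cost is one survey link and one short question with its reason. Some self-entries will be missed. Guesses will partly reflect benefit, which is why the reason is asked. Precision of about ±20 to 22 percentage points per arm will show only a gross failure of blinding. Self-entry removes the interviewer from the primary score, but it does not remove the patient's own expectation; the guess question only makes that visible.

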6.6.1. General

The numerical pain scale will be administered verbally during each study visit.

Study staff will ask both average and worst pain experienced in the week prior to each study visit, using the same Numerical Rating Scale. Additionally, she will ask if and for how long relief lasted after QUELL FLEX use on average over the week.

